4.3 Study Enrollment Procedures

Recruitment will occur by way of flyers placed in well-trafficked areas, information sheets provided to potential participants, and clinician referral at partner practices. Women who express interest will be contacted by a study staff member to arrange for a virtual meeting (by phone or video) to obtain consent and complete the baseline assessment, if eligible. Consented participants will then be randomized, by the lead project coordinator using a standard randomization process, in equal proportions to receive the intervention (MMORE) or treatment as usual condition. The lead project coordinator will meet virtually with participants to explain the study procedures and provide instructions to the digital support features (Intervention Only).

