9.2 Sample Size and Randomization

Sample Size.

Aim 1: For the longitudinal models of binary outcomes (abstinence, retention), assuming a within-person correlation of 0.5, there will be 80% power to detect difference between arms in the proportion retained at the 3 timepoints if the average percentage retained in the TAU arm is 60%, and the average percentage retained in the MMORE arm is 79.2%. Similar power is obtained if the TAU arm has a retention percentage of 70% while the MMORE arm has a percentage of 87% across the three timepoints. In terms of comparing abstinence longitudinally, there will be 80% power to detect a difference between arms in the percentage abstinent at the 3 timepoints if the average percentage abstinent in the TAU arm is 80% while in the MMORE arm is 94%. Power for the comparison of number of weeks abstinent during the 8-week intervention period will be 80% (at the two-sided 0.05 significance level) for differences between arms that are 0.52 times a standard deviation or more. Analyses testing for differences between arms in changes between baseline and 8-weeks, will have 80% power to detect differences that are 0.40, 0.52, and 0.61 times a standard deviation, assuming within-person correlations of 0.7, 0.5, and 0.3, respectively. We will aim to recruit 150 participants to allow for attrition (20%).

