Aim 2: For examining mediation/mechanistic effects at the individual-level from longitudinal data via parallel process growth models (paths from treatment assignment to individual-level slope of mediator to individual-level slope of outcome), with 120 individuals, there will be 80% power to detect indirect effects comprised of a small-medium effects of the intervention arm on latent slope of mindfulness (defined as a correlation of 0.25 between variables or equivalently as explaining 6% of the variance in the latent mindfulness slope) and a medium effect of the slope of mindfulness on the slope of the outcome (defined as a correlation of 0.36 or equivalently as explaining 13% of the variance of the outcome). For examining mediation/mechanistic effects at the weekly level, power is less clear. Although DSEM combines aspects of more familiar modeling techniques, it is new and thus limited information is available on determining power for such models. In one set of simulation studies, good model performance was observed for several models differing in complexity for a sample size of 200 individuals with a number of observations per individual ranging from 20-200, and good model performance for all but the most complex models for smaller sample sizes. Thus, with data from 120 individuals contributing up to 8 observations each, we expect to have enough data to accomplish the aim of understanding the mechanisms underlying the intervention effects of MMORE. We will conduct weekly assessments to minimize participant burden. This strategy will still allow us adequate sampling frequency to track changes in outcome measures over the course of treatment. The power

calculations for the mechanistic effects were based on individual-level latent slope variable estimates and are thus not affected by a change to the number of indicator variables for the latent slope variables (reduced from 70 daily assessments to 8 weekly assessments). Power calculations for the dynamic SEM models are approximate and were not specifically based on having daily assessments per individual so will also not change.

Aim 3 is exploratory and not powered.

Treatment Assignment Procedures

Randomization will be conducted via permuted blocks. Once 8-10 participants have enrolled, an intervention will commence for that cohort. The randomization block size would be random, with blocks of size 4, 6, and 8. We plan ongoing recruitment and to start a new group approximately every 8 weeks.

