9.6 Data Analyses

Aim 1

Primary analysis: The difference between treatment arms with respect to likelihood of opioid abstinence and remaining in treatment will be evaluated by logistic generalized estimating equations (GEE). Since these binary outcomes will be evaluated at the 8-week as well as the 3-month postpartum time points, these GEE models will account for the non-independence of repeated measurements within individual. An indicator of treatment arm, time point, as well as an interaction between treatment and time point will be included as predictors in the model along with baseline covariates. Significant differences between the arms will be tested via contrasts involving the treatment*time point interaction term that compare the outcomes at each time point.

The impact of *MMORE* on treatment retention (number of weeks retained) will be evaluated via two-sample t-test if the distribution appears symmetric, but a non-parametric Wilcoxon rank sum test will be used otherwise.

Aim 2

Primary analysis: Analyses of mechanisms of effect of *MMORE* will be performed via parallel process growth models fit via structural equation models, and mediated effects between treatment assignment and outcome will be examined for the following mediator-outcome pairs: craving-abstinence, mindfulness-craving, mindfulness-treatment retention, depression-treatment retention, anxiety-treatment retention, stress-treatment retention, and mindfulness-pain. Since each mediator and outcome variable will be collected at multiple time points, latent intercept and slope effects can be estimated (as in latent growth curves). The parallel process growth models then examine mediation of the effect of an individual-level variable (treatment assignment) on the latent slope of the outcome variable by the latent slope of the mediator variable. For each mediator-outcome pair, a parallel process growth curve model will be fit including both the direct effect of treatment assignment to *MMORE* on the latent slope of the outcome, as well as the indirect effect of *MMORE* on slope of the outcome through the slope of the mediator. Estimates of path coefficients for each individual path as well as of the indirect effect along with a 95% bootstrap confidence interval will be obtained.

To examine these associations we will implement a newly developed modeling strategy called dynamic structural equation models (DSEM). DSEM like non-dynamic SEM are a modeling

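### The Aim 2 growth models name no baseline covariates, so a baseline factor that drives both slopes could be reported as a mechanism of MMORE

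*Combined protocol and SAP*

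**What the plan says.** Section 9.6, Aim 2, lists seven mediator-outcome pairs: craving-abstinence, mindfulness-craving, mindfulness with retention, depression, anxiety and stress each with retention, and mindfulness-pain. For each, "a parallel process growth curve model will be fit including both the direct effect of treatment assignment" on the outcome slope, together with the indirect effect through the mediator slope. Path estimates and the indirect effect "along with a 95% bootstrap confidence interval will be obtained". Latent intercepts are mentioned as estimable, but their relation to the slopes is not described.

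No baseline covariate, no assumption about mediator-outcome confounding and no sensitivity analysis for it appears in section 9.6 Aim 2 or in the Aim 2 part of section 9.2. By contrast, in the Aim 1 GEE the arm, time and interaction terms "will be included as predictors in the model along with baseline covariates". Those covariates are not named.

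Section 9.2 states that "with 120 individuals, there will be 80% power to detect indirect effects". The arm-to-mediator path is "defined as a correlation of 0.25 between variables" and the mediator-to-outcome path is "defined as a correlation of 0.36".

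**The concern.** Women are allocated "in equal proportions to receive the intervention (MMORE) or treatment as usual condition" (section 4.3). That protects the arm-to-mediator path. It does not protect the mediator-to-outcome path, because nobody is randomised to a mediator slope. A baseline characteristic that makes craving, mood or stress improve more slowly and also makes retention or abstinence worse will link the two slopes even if the mediator has no effect.

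The protocol's own background makes such common causes plausible. Section 2.1 ties mental health to the experience of pain, and under-treated pain to relapse; section 2.2 notes that many of these women have experienced trauma. The bootstrap interval reflects sampling error only, so it cannot reveal this bias. Section 1.2 gives Aim 2 the task of pointing to intervention targets, so a confounded path could send later work after the wrong one.

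**Working it through.** **Inputs from the plan.** N = 120 analysed (150 recruited, 20% attrition: 150 × 0.80 = 120); 1:1 allocation; arm-mediator correlation a = 0.25; mediator-outcome correlation 0.36; 95% interval for the indirect effect.

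**Assumed, because the documents give no figure.** A baseline factor has the same correlation c with both slopes, c from 0.2 to 0.5. The true mediator effect is zero. Slopes are treated as observed.

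**1. Reproduce the plan's power.** A single-mediator simulation of 3,000 trials, with 0.25 and 0.36 read as partial correlations, gives 80.2% by percentile bootstrap and 79.6% when both paths must be significant. The stated 80% is reproduced, by a model with no confounder of the second path.

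**2. Spurious mediator-to-outcome coefficient.** Given arm, the covariance of the two slopes is c² and the variance of the mediator slope is 1 − 0.25² = 0.9375. So b = c²/0.9375, and the partial correlation is r = c²/√0.9375.

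**3. Chance of a false indirect effect, in closed form.** Both paths must be significant.
- Arm path: atanh(0.25) × √117 = 2.763, giving power 0.789.
- Mediator path: z = atanh(r) × √116, giving power Φ(z − 1.96) + Φ(−z − 1.96).
- The false rate is approximately the product of the two.

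| c | spurious b | r | z | mediator path significant | × 0.789 |
|---|---|---|---|---|---|
| 0.2 | 0.043 | 0.041 | 0.445 | 0.073 | 5.8% |
| 0.3 | 0.096 | 0.093 | 1.004 | 0.171 | 13.5% |
| 0.4 | 0.171 | 0.165 | 1.796 | 0.435 | 34.3% |
| 0.5 | 0.267 | 0.258 | 2.845 | 0.812 | 64.1% |

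**4. Simulation, 4,000 trials per setting.**

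| c | no covariates | slopes regressed on intercepts only* | adjusted for the factor | no covariates, arm does not move mediator |
|---|---|---|---|---|
| 0.2 | 5.6% | 4.0% | 3.4% | 0.2% |
| 0.3 | 13.5% | 7.9% | 3.9% | 1.1% |
| 0.4 | 35.1% | 17.1% | 4.0% | 2.3% |
| 0.5 | 66.2% | 39.6% | 4.4% | 3.6% |

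*Intercepts assumed to correlate 0.5 with the factor.

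A Monte Carlo 95% interval for the product of the paths, in place of joint significance, gives 13.2%, 34.7% and 64.5% at c = 0.3, 0.4 and 0.5. It gives 3.7% with no confounding, and 3.9% to 4.8% after adjustment.

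**5. Sensitivity to the assumptions.**
- Correlations of 0.3 with one slope and 0.1 with the other: about 5%.
- Slope reliability 0.7 (regression approximation): about 7%, 14-15% and 32-34% at c = 0.3, 0.4 and 0.5.
- Slope reliability 0.5: about 4%, 7% and 14%.

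**The case against.** The strongest reply is that the plan is silent and does not exclude covariates. Section 9.6 says what the model includes, and that need not be a complete list. This is right, and a reader should not infer that the sponsor has chosen to leave covariates out or to keep slopes unrelated to intercepts. The gap still matters: nothing fixes the adjustment set before the data are seen, across seven pairs. Intercepts alone would not close it; in the check above they leave false rates of up to about 40%.

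A reader might also extend the point to all of Aim 2. The documents do not support that. The DSEM in section 9.6 separates each woman's stable level from her weekly deviations, so stable baseline severity is largely removed from the within-person paths. Individual-level variables are also allowed in its between-individual part, although only arm is named.

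Nor do the rates predict what will happen in this trial. The correlations are assumed, and they are with rates of change rather than levels. The result is close to nominal at 0.2, lower with unequal correlations or noisy slopes, and requires a real effect of arm on the mediator. Several outcomes have only three assessments (section 6.1), so unreliable slopes are likely.

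Finally, no adjustment removes unmeasured confounding, and Aim 2 does not alter the Aim 1 efficacy comparison. Both statements are true; they are reasons for a sensitivity analysis and for moderate priority.

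**Conclusion.** The point holds for the parallel process growth models. As written, they can report mediation where there is none. At the plan's sample size and arm effect the false rate is about 6%, 13%, 35% and 65% for assumed equal correlations of 0.2, 0.3, 0.4 and 0.5, and about 3-5% once the factor is adjusted for. At 0.4 the spurious coefficient of 0.17 is nearly half the 0.36 for which the analysis is powered (0.17/0.36 = 0.47).

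These figures rest on a true mediator effect of zero, a real arm-to-mediator correlation of 0.25, and slopes treated as observed, which puts them towards the upper end. It is tempting to say that Aim 2 should simply reuse the Aim 1 covariates, but the plan leaves those unnamed, so there is no list to carry over. The change should be made, but the main efficacy test does not depend on it.

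**What to change.** In section 9.6, Aim 2:

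- Prespecify a short common set of already collected baseline covariates as predictors of both latent slopes, for example depression, posttraumatic stress, pain and opioid use disorder severity. All four are described in the section 6.2 survey; the section 6.1 schedule has rows for depression and pain only, so confirm that the other two are taken at baseline.
- Omit from any pair a covariate that is the first wave of that pair's own mediator or outcome: depression in depression-retention, pain in mindfulness-pain. Otherwise it enters twice, once as covariate and once through the intercept.
- Regress slopes on the intercepts where these are identified and have variance. All women are on MOUD at entry (sections 4.1 and 5.3.2), so a retention intercept may have little or none.
- Report how large a residual mediator-outcome slope correlation would remove each indirect effect, and describe indirect effects as conditional on no remaining confounding.
- Do not present the list as the Aim 1 covariates.

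The cost is SAP wording, with no new data collection if the baseline timing is confirmed. Four covariates on two slopes add 8 paths, and two intercepts on two slopes up to 4 more, so at most 12 per model. With 120 women that means a small loss of precision, and it is the reason to keep the set short.

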framework that allows for estimating simultaneous sets of equations involving latent and observed variables, thus allowing modeling of multi-level data, and modeling relationships at each level including mediation. Unlike non-dynamic SEM, however, DSEM have the capability to estimate time-series model(s) at the within-individual level, and also allow for a between-time level model (in addition to the between-individual level model) to incorporate time-varying effects observed in intensively collected data (i.e. creating a cross-classified model). Thus DSEM combine the advantages of time-series models, multi-level models, time-varying effect models, and other SEM, and importantly for the current application allows examination of relationships between multiple intensively collected variables (here affective state, mindfulness, stress, and craving) as well as moderation of these relationships by both individual-level (here treatment arm) and daily-level (session attendance, mindfulness) variables. The DSEM is specified by models at three levels. The three-level specification results from a decomposition of the observed variable(s) for a given individual at a given time (vector Y_{it}^*) into three latent, unobserved parts: an individual-specific contribution $Y_{2,i}$ a time-specific contribution $Y_{3,t}$ and a deviation for an individual, at a given time $Y_{1,it}$ ($Y_{it}^* = Y_{1,it} + Y_{2,i} + Y_{3,t}$). For example, for stress, observed weekly stress ($dStr_{it}^*$), becomes: $dStr_{it}^* = dStr_{it} + Str_i + Str_t$. These three latent components are then modeled simultaneously in a within-individual, between-individual, and between-time model. The time series describing the relationship between past and current observations in one or more intensively collected variables is modeled at the within-individual level (detailed below) The between-individual model examines influences on mean weekly stress (Str_i) and mean weekly craving as well as influences on individual-level random effects specified in the within-individual model (e.g. $\varphi_{SC,i}$: representing the relationship between weekly craving and weekly stress). The between-time model examines influences on the mean daily stress at a given time (Str_t) and on mean weekly craving at a given time (as well as influences on time-specific random effects specified at the within-individual model). For the current application, one within-individual model is a bivariate autoregressive (here specified with a lag of 1 but other lags will be explored) of weekly stress ($dStr_{it}$) and weekly craving (dCr_{it}).

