
$$\begin{aligned} dStr_{it} &= \varphi_{SS,i} dStr_{it-1} + \varphi_{SC,i} dCr_{it-1} + \zeta_{S,it} \\ dCr_{it} &= \varphi_{CC,i} dCr_{it-1} + \varphi_{CS,i} dStr_{it-1} + \zeta_{C,it} \end{aligned}$$

We will obtain an estimate of the relationship between the current value of dCr and lagged value(s) of dStr ($\varphi_{CS,i}$). Moderation of this relationship by immediate contextual variables (such as weekly mindfulness value, mindfulness session attendance (among those on MMORE arm)) can be examined by including an interaction between time-varying context variables and dCr in the dStr equation. Since the regression parameters estimated are considered random individual effects, associations with other individual-level variables (such as treatment arm assignment) can be modeled in the between-individual model. This will allow us to examine moderation of the weekly relationship between dStr and dCr by individual-level variables. Mediation of the effect of immediate contextual variables on mRB by mSR will be evaluated using a cross-lagged mediation model.

Aim 3 (Exploratory). Quantitative data will be descriptively summarized, and qualitative data coded for salient themes using standard deductive methods described earlier. Data summaries will be reviewed by the Steering Committee and consultants to inform strategies to support dissemination and sustainable implementation of MMORE in women's health care settings. Data will guide interpretation of participant outcomes.

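### The Aim 2 DSEM has no woman-specific time trend although the Aim 2 growth models assume one, so its autoregressions are inflated and its cross-lags can be biased in either direction

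*Combined protocol and SAP*

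**What the plan says.** Section 9.6 (Data Analyses, Aim 2) describes two analyses.

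The first is a set of parallel process growth models. Each mediator and outcome has a latent intercept and slope, and the models test "mediation of the effect of an individual-level variable (treatment assignment) on the latent slope of the outcome variable" through the latent slope of the mediator. Craving and stress both appear in the listed mediator-outcome pairs (craving with abstinence, mindfulness with craving, stress with treatment retention). Section 9.2 confirms that the slope indicators are now the 8 weekly assessments, with 120 women.

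The second is the dynamic structural equation model (DSEM), introduced as a way to examine these associations. For stress the decomposition is "dStr_{it}^* = dStr_{it} + Str_i + Str_t". The section continues: "These three latent components are then modeled simultaneously in a within-individual, between-individual, and between-time model". The deviations follow a bivariate autoregression, "here specified with a lag of 1 but other lags will be explored". At the woman level, "The between-individual model examines influences on mean weekly stress (Str_i) and mean weekly craving", together with the random autoregressive and cross-lag effects. The between-time level gives each week an effect common to all women. The named result is the stress-to-craving cross-lag, phi_CS: "We will obtain an estimate of the relationship between the current value of dCr and lagged value(s) of dStr". Its moderation by treatment arm is built on that coefficient.

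The section mentions no woman-specific or arm-specific trend, no detrending step and no check of stationarity.

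**The concern.** The two Aim 2 analyses make incompatible assumptions about the same kind of weekly series. If women change at different rates, as the growth models suppose, the DSEM has nowhere to put those differences. The constant level Str_i cannot hold a slope, and Str_t holds only the slope that all women share. What remains falls into the within-woman deviations, which the model treats as a stationary process. A slow individual drift then looks like week-to-week persistence. If the drifts in stress and craving are related across women differently from the weekly fluctuations, it also looks like one variable predicting the other a week later.

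At stake is the interpretation of phi_CS, the DSEM result the plan names. The Aim 1 efficacy comparison is not affected.

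**Working it through.** **The plan's own figure.** Section 9.2 states 80% power for the growth-model indirect effect with 120 women and path correlations 0.25 and 0.36. Simulation (4,000 runs, two-sided 5%) gives 79.2% by joint significance and 79.8% by a 95% interval for the product, so the figure reproduces. Recruitment also agrees: 150 × 0.8 = 120. No power or error rate is stated for the DSEM.

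**Inputs.** From section 9.2: 120 women, 8 weekly observations. Assumed, because the documents do not give them for stress and craving:
- D, the SD across women of individual change from week 1 to week 8, in within-person SDs: 0.5, 1.0, 1.5.
- ρ, the correlation between a woman's stress slope and her craving slope: 0.36 (borrowed from the slope-to-slope path in section 9.2, which concerns mindfulness) or 0.6.
- c, the same-week residual correlation of stress and craving: 0, 0.2, 0.36, 0.5.
- True autoregression φ = 0.3 for both variables; true cross-lags 0.

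**Direction.** After the level and common week effect are removed, the deviation is a stationary part plus slope × centred week. Let a′ and a be the trend's contribution to the lag-0 and lag-1 covariances. The lag-1 coefficient matrix is then roughly (φR_c + aR_ρ)(R_c + a′R_ρ)⁻¹, where R_r is the 2×2 correlation matrix with off-diagonal r. Its eigenvalues are

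λ± = [φ(1±c) + a(1±ρ)] / [(1±c) + a′(1±ρ)].

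The autoregression is (λ₊ + λ₋)/2 and each cross-lag is (λ₊ − λ₋)/2. Each λ is a weighted average of φ and a/a′. Centring the weeks at 4.5, the mean square is 42/8 = 5.25 and the mean lag-1 product is 26.25/7 = 3.75, so a/a′ = 3.75/5.25 = 0.71, above 0.3. Therefore:
- autoregression is always inflated;
- the two cross-lags are equally distorted;
- the false cross-lag is positive if ρ > c, zero if ρ = c, negative if ρ < c.

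**Size.** This approximation is used only for direction. Sizes come from maximising the expected normal likelihood of the written model (random intercepts, free week means, bivariate lag-1 autoregression with phi fixed across women). With z = |phi_CS|/SE, the false-positive rate is Φ(z − 1.96) + Φ(−z − 1.96).

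Results at ρ = 0.36, for D = 1.0 / 1.5:

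| c | fitted phi_CS | SE | false-positive rate |
|---|---|---|---|
| 0 | 0.037 / 0.070 | 0.039 | 16% / 44% |
| 0.2 | 0.017 / 0.032 | 0.040 | 7% / 13% |
| 0.36 | 0.000 / 0.000 | 0.042 | 5% / 5% |
| 0.5 | −0.019 / −0.036 | 0.044 | 7% / 13% |

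For example, c = 0.2 and D = 1.5 gives z = 0.032/0.040 = 0.80 and Φ(−1.16) + Φ(−2.76) = 0.123 + 0.003 = 13%. At ρ = 0.6, over the same c and D = 1.0 to 1.5, the rate runs from 6% (c = 0.5, D = 1.0) to about 85% (c = 0, D = 1.5). Across D = 0.5 to 1.5 the autoregression is read as 0.33 to 0.54 against a true 0.30.

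**Simulated fits.** A separate simulation (400 data sets per scenario, models refitted to each) gave somewhat smaller rates at ρ = 0.36: with c = 0, 12% at D = 1.0, 33% at D = 1.5 and 50% at D = 2.0; with c = 0.3 and D = 1.5, 8%. With random slopes added, mean phi_CS was −0.002 to 0.002 and the false-positive rate 3.5% to 7.0%.

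**The case against.** The strongest reply is that the size, and even the sign, of any false cross-lag rests on quantities the documents never state. That stands. The largest rates require c = 0, meaning that a woman's stress and craving are unrelated within the same week, and nothing in the documents supports that. At ρ = 0.36 with c between 0.2 and 0.5, the rate does not exceed 13% even at D = 1.5. The correlations 0.25 and 0.36 are stated for mindfulness paths, and stress-craving is not one of the listed mediator-outcome pairs. The plan therefore does not itself assume correlated stress and craving slopes.

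A second reply is that the DSEM text is illustrative: the autoregression is offered as one within-individual model, other lags are allowed, and time-specific random effects are mentioned. So a trend is not excluded, but none is written, and neither other lags nor effects common to all women in a week supply a woman-specific slope.

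A third reply is that detrending may remove part of the treatment signal if gradual change is the mechanism. This has some force. However, a trend whose mean depends on arm keeps that signal in the model as an arm effect on slope, and leaves phi_CS to describe week-to-week coupling, which is what the lagged equations are for.

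**Conclusion.** The omission is real: under the growth models' own premise, the DSEM as written is misspecified. If women's slopes vary, autoregression is overstated in every scenario examined. Both cross-lags can be biased in either direction, with false-positive rates for phi_CS from nominal (5%) to about 85% over the assumed ranges.

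A reader might infer that the DSEM will show stress driving next-week craving. The documents do not support that. The bias can be zero or negative, it affects the craving-to-stress path equally, and a decline shared by all women is absorbed by the week effect. A reader might also infer a false arm difference in phi_CS. That would need slopes to vary more among MMORE women than TAU women, which the documents do not say. Nor does an arm difference in mean slope do much by itself to phi_CS: 0.5 within-person SD over 8 weeks leaves its false-positive rate at about 5%, and 1.0 SD gives 7% to 10%.

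The figures come from a likelihood analogue with phi fixed across women and complete data, not from the random-phi DSEM itself. They show that the problem can matter, not how large it will be in this trial. It should be settled before analysis, since the data-generating correlations cannot be known beforehand.

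**What to change.** In section 9.6, add to the DSEM a woman-specific linear week term for stress and another for craving, with their means regressed on treatment arm. Base phi_CS, and its moderation by arm, on that model. Keep the model without trends as a sensitivity analysis and report both.

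The cost is a few more parameters (two random slopes, their covariance and the arm effects) and a less precise cross-lag. In the same likelihood calculation at c = 0 and D = 1.0, the SE of phi_CS rises from 0.039 to 0.047 (0.047/0.039 = 1.21, about 20%), while phi_CS returns to 0 and the autoregression to 0.30. No data collection changes.
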